ABC-I	Aberrant Behavior Checklist- Irritability Subscale
[REDACTED]	[REDACTED]
[REDACTED]	[REDACTED]
AE	Adverse Event
AGG_MENT	Aggregate Mental
AGG_PHYS	Aggregate Physical
ANCOVA	Analysis of Covariance
ANOVA	Analysis of Variance
AS	Angelman Syndrome
ATC	Anatomical Therapeutic Class
BID	Bis in die in Latin meaning twice a day
BMI	Body Mass Index
BP	Bodily pain
bpm	Beats per minute
[REDACTED]	[REDACTED]
CGI-I	Clinical Global Impressions-Improvement
CGI-S	Clinical Global Impressions-Severity
[REDACTED]	[REDACTED]

CI	Confidence Interval
cm	centimeter
COA	Clinical Outcome Assessments
CRF	Case Report Form
CSR	Clinical Study Report
EEG	Electroencephalogram
EQ-5D-5L	EuroQOL-5L
FAS	Full Analysis Set
GH	General health
HLGT	High Level Group Term
HLT	High Level Term
ICF	Informed Consent Form
ICH	International Conference on Harmonisation
ITT	Intent-to-Treat
IWRS	Interactive Web Response System
kg	Kilograms
MCS	mental component scores
MedDRA	Medical Dictionary for Regulatory Activities
mg	milligram
mmHG	Millimeter of mercury
MH	Mental health
MMRM	Mixed Model Repeated Measures

[REDACTED]	[REDACTED]
[REDACTED]	[REDACTED]
NA	Nocturnal Awakenings
ODS	Output Delivery System
PCS	physical component scores
[REDACTED]	[REDACTED]
PGI	Parent's Global Impression
PF	Physical functioning
PP	Per Protocol
PT	Preferred Term
Q1	Quartile 1
Q3	Quartile 3
QD	Quaque die in Latin meaning one a day
RE	Role limitations due to emotional problems
RP	Role limitations due to physical health
RTF	Rich Text Format
SAP	Statistical Analysis Plan
SAS	Statistical Analysis System
sec	second
SF	Social functioning
[REDACTED]	[REDACTED]

[REDACTED]	[REDACTED]
SOC	System Organ Class
SOL	Sleep Onset Latency
SS	Safety Set
TEAE	Treatment Emergent Adverse Event
TST	Total Sleep Time
USA	United States of America
VT	Vitality
WASO	Wake After Sleep Onset

1 INTRODUCTION

This Statistical Analysis Plan (SAP) describes the data-handling and statistical procedures to be used for the statistical analysis and reporting of efficacy and safety data collected under the Ovid Protocol OV101-15-001 Amendment 3 (September 7, 2017). The methods of analysis in this SAP expand on statistical considerations identified in the protocol; where considerations are substantially different, they will be identified as such in this document. This SAP has been developed and finalized prior to locking the clinical database for the primary analysis. Any additional analyses required to supplement the analyses specified in this SAP will be considered exploratory and will be identified in the Clinical Study Report (CSR).

The SAP was written in accordance with the recommendations outlined in the International Conference on Harmonisation (ICH) E9 Guideline entitled “Guidance for Industry: Statistical Principles for Clinical Trials” and the most recent ICH-E3 Guideline entitled “Guidance for Industry: Structure and Content of Clinical Study Reports.”

2 STUDY SUMMARY

2.1 STUDY OBJECTIVES

The primary objective of the study is to evaluate the safety and tolerability of OV101 from Baseline to Week 6 and Week 12 in adult and adolescent subjects with Angelman Syndrome (AS) across different dose levels and in 2 dosing schedules.

The following dosing schedules will be assessed against placebo:

- Once daily (QD): Morning dose of placebo and an evening dose OV101 titrated to the target dose of 15 mg unless not tolerated
- Twice daily (BID): Evening and morning doses of OV101 titrated to the target doses of 15 mg evening dose and 10 mg morning dose unless not tolerated.
- Placebo only: Evening and morning dose of placebo.

The secondary objective is the identification of a set of parameters that may best characterize the efficacy of OV101 in adult and adolescent AS subjects for subsequent efficacy studies. These clinical outcomes assessments (COA) are administered at 3 full day study center visits (Baseline, Interim, and End of Treatment) by an appropriately trained professional to the adult and adolescent AS subjects or their caregivers, as appropriate. Assessments are based on direct observation from study center personnel observations and/or caregiver(s).

[REDACTED]

[REDACTED]

2.2 STUDY DESIGN

This is a multicenter, Phase 2, randomized, parallel (3 arm), double-blind, placebo-controlled study of OV101 in adult and adolescent subjects with AS to assess safety of OV101. Multiple efficacy endpoints are assessed to identify the most appropriate and sensitive outcome measures for future efficacy studies. The study compares 3 different treatment/dosing schedules (15 mg evening dose only [QD], 15 mg evening dose plus 10 mg morning dose [BID], or placebo) for 12 weeks.

[figure not shown]
Approximately 75 subjects will be enrolled at approximately 15 study centers in the United States of America (USA) and Israel. At the completion of the study, there will be approximately 25 subjects in each of the 3 treatment groups: A) single evening dose, B) morning and evening dose, and C) placebo.

Adults aged 18 to 49 years and adolescents aged 13 to 17 at the time of informed consent with a molecular confirmation of AS are eligible for inclusion.

The study comprises a screening period of up to 4 weeks; a baseline visit for treatment randomization; a 12-week treatment period comprised of a 14-day titration period where treatment doses are progressively increased and a 6-week and 12-week visit for safety and efficacy assessments. The final study visit is for the end of treatment visit procedures followed by a 2-week telephone follow-up period to monitor safety.

All subjects receive a morning dose and an evening dose during the entire duration of treatment. Doses are progressively increased in 5 mg increments (OV101 or Placebo) to a target of 15 mg (3 capsules) in the evening for the OV101 groups and 10 mg (2 capsules) in the morning for the OV101 BID group. This up-titration to the target dose occurs unless this target dose is not tolerated. All subjects receive treatment for a maximum of 12 weeks at their highest tolerated dose. Modifications may be made per investigator judgement on urgent need or medical necessity. If tolerability is not acceptable after a previous up-titration step or during the course of the 12 weeks of

treatment, dose can be reduced to the previous tolerated level or even further. Once the tolerable dose has been reached, it shall remain constant for the duration of the treatment period.

*to end of study treatment period

2.2.1 Number of Subjects

Approximately 75 subjects will be enrolled and randomized into one of 3 treatment groups:

- OV101 QD: morning dose of placebo and evening dose of OV101
- OV101 BID: morning and evening dose of OV101
- Placebo: morning and evening dose of placebo

[figure not shown]
2.2.2 Randomization and Blinding Procedures

Subjects are randomized centrally via Interactive Web Response System (IWRS) with a 1:1:1 treatment allocation. Investigators, study staff, and study subjects are blinded to the randomized study treatment assignments.

2.2.3 Exploratory Efficacy Assessments

■ [REDACTED] ■ [REDACTED] ■ [REDACTED]

A 6x6 grid of 36 black rectangles of varying widths and heights on a white background. The rectangles are arranged in a staggered, non-overlapping pattern. The widths range from 1 to 6 rectangles across the grid. The heights range from 1 to 6 rectangles down the grid. The pattern is: Row 1: 1, 2, 3, 4, 5, 6. Row 2: 2, 3, 4, 5, 6, 1. Row 3: 3, 4, 5, 6, 1, 2. Row 4: 4, 5, 6, 1, 2, 3. Row 5: 5, 6, 1, 2, 3, 4. Row 6: 6, 1, 2, 3, 4, 5.

2.2.4 Safety Assessments

- Adverse Events (AE) collected continuously throughout the study
- Physical Examinations collected at Baseline, Day 43 (week 6) and Day 84 (week 12)
- Vital Signs collected at Baseline, Day 43 (week 6) and Day 84 (week 12)
- Laboratory parameters (electrolytes, lipids, glucose, renal, hepatic and pancreatic function tests, and hematology) collected at Baseline, Day 43 (week 6) and Day 84 (week 12)
- Electroencephalogram (EEG) collected at Baseline and Day 84 (week 12)
- Suicidality measured by the irritability sub-scale from the community ABC-C scale is collected at Baseline, Day 43 (week 6) and Day 84 (week 12)
- Caregivers' electronic seizure diary (Note: any clinically important changes, including changes in seizure medication, is reported as a safety event)

2.2.5 Other Assessments

- Concomitant Medications collected continuously throughout the study
- Blood draws for Biomarkers that will be evaluated externally

Table 1 Schedule of Assessments

Visit Name	Screening	Baseline	Unscheduled	Phone Titrate	Phone Safety	Interim	Phone Safety	End of Treatment	Follow-up Phone*
Window			Any Time	+2 Days	± 2 Days	± 3 Days	± 2 Days	+ 3 Days	± 2 Days
	D-28 to D 0	D 1	Any Time	D 3, 7, 10, 14	D 31	D 43	D 57, 71	D 84	D 98
Week		1				6		12	14
ICF and Assent (Separate for Caregiver and Subject)	X								
Inclusion/Exclusion Criteria	X	X							
Medical History	X	X							
Clinical Assessment [†]	X	X		X	X	X	X	X	X
Biomarker Plasma [‡]		X							X
Biomarker DNA [‡]		X							
Molecular AS Test [§]	X								
Dose Titration				X	X [#]	X [#]	X [#]		
Physical Exam	X	X				X		X	
Vital Signs	X	X				X		X	
Clinical Laboratory Tests	X	X				X		X	
Serum Pregnancy Test ^{**}	X	X				X		X	
EEG		X						X	
Adverse Events	X	X	X	X	X	X	X	X	X
Concomitant Medications	X	X	X	X	X	X	X	X	X
Check Scales Completed by Clinician:									
CGI-S scale (in Sub-Domains and Global)			X				X		X

	CGI-I scale (in Sub-Domains and Global)		X					X		X	
	[REDACTED]		[REDACTED]							[REDACTED]	
	[REDACTED]		[REDACTED]							[REDACTED]	
	ABC-I (ABC-C Irritability Subscale)	See Caregiver ABC-C (Factor I) Score	X	X	X	X	X	X	X	X	X
Check Scales Completed by Caregiver:											
	[REDACTED]		[REDACTED]	[REDACTED]				[REDACTED]		[REDACTED]	
	[REDACTED]		[REDACTED]	[REDACTED]				[REDACTED]		[REDACTED]	
	CGI-S	X	X					X		X	
	[REDACTED]		[REDACTED]	[REDACTED]				[REDACTED]		[REDACTED]	
	[REDACTED]		[REDACTED]	[REDACTED]				[REDACTED]		[REDACTED]	
	[REDACTED]		[REDACTED]	[REDACTED]				[REDACTED]		[REDACTED]	
	[REDACTED]		[REDACTED]	[REDACTED]				[REDACTED]		[REDACTED]	
	[REDACTED]		[REDACTED]	[REDACTED]				[REDACTED]		[REDACTED]	
	[REDACTED]		[REDACTED]	[REDACTED]				[REDACTED]		[REDACTED]	
	eDiary of Sleep Pattern ⁺⁺	X	X					X		X	
	eDiary of Seizure Activity ⁺⁺	X	X					X		X	
	eDiary of Medication Compliance ⁺⁺			X				X		X	
Check Other Assessments Completed											
	[REDACTED]		[REDACTED]							[REDACTED]	
	[REDACTED]		[REDACTED]					[REDACTED]		[REDACTED]	

Abbreviations: ABC-C = Aberrant Behavior Checklist – Community; ABC-C-Irritability Subscale = Aberrant Behavior Checklist – Community – Irritability Subscale; [REDACTED]
[REDACTED] CGI-I = Clinical Global Impression – Improvement; CGI-S = Clinical Global Impression –
Severity; [REDACTED] EEG = Electroencephalogram; [REDACTED] ICF = Informed Consent Form; [REDACTED]

* Safety follow-up phone visit 2 weeks after End of Treatment.

† Signs and symptoms of the syndrome.

‡ Only if separate ICF was signed.

§ Only if no written evidence for molecular diagnosis in subject records available.

Ongoing up-titration if target dose could not be reached until Day 14. Down-titration for non-tolerability should be discussed with the Sponsor MM or his/her delegates if necessary.

**For women of child-bearing potential.

††Continuous use and documentation; [REDACTED] electronic subject reported outcomes data will be downloaded by study center staff at baseline, interim, and End of Treatment visits.

3 STATISTICAL METHODS

3.1 General Methods

All statistical analyses will be performed using SAS® Version 9.4 or higher for Windows.

All clinical study data will be presented in subject data listings. In by-treatment group descriptive presentations, the 3 randomized treatment groups (15 mg evening dose only [QD], 15 mg evening dose plus 10 mg morning dose [BID], placebo) will be presented separately as well as a combined treatment group for OV101 QD and BID dosing.

Descriptive statistics (n, mean, standard deviation, Q1, median, Q3, minimum, and maximum) will be calculated by treatment group for continuous variables. Confidence intervals will be provided where appropriate.

Frequencies and percentages will be presented by treatment group for categorical variables. If there are missing values, the number missing will be presented, but without a percentage.

Means, medians, and confidence intervals will be reported to one decimal place more than the data reported on the Case Report Form (CRF) or by the laboratory/vendor. Standard deviations will be reported to two decimal places more than the data reported. Minimum and maximum will be reported to the same number of decimal places displayed on the CRF or by the laboratory/vendor. P-values will be reported to 4 decimal places.

Unless otherwise specified, all tests will be 2-tailed using a 0.05 level of significance. All confidence intervals (CIs) will be 2-sided 95% CIs.

3.1.1 Baseline Value and Change from Baseline (if applicable)

A Baseline value is defined as the most recent non-missing value obtained immediately prior to administration of first dose. Change from baseline will be calculated by subtracting the baseline value from the post-dose assessment for each subject (i.e., post-dose – baseline).

3.1.2 Handling of Missing/Incomplete Values

Selected efficacy analyses of Week12 endpoints will include missing value adjustments, if possible, by using the corresponding Week 6 observations either implicitly (in MMRM analyses) or by simple imputation (for binary endpoints).

These selected analyses are detailed below. For all other analyses, observed case data will be used and no imputations for missing data will be performed.

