8. Unless otherwise specified, the estimated mean and median for a set of values should be printed out to one more decimal place than the raw (observed) data and rounded appropriately. Standard errors (or standard deviations) should be printed out to two additional decimal places than the raw (observed) data and rounded appropriately. For example, for age (with raw data in whole years):

n	xx
Mean (SD)	xx.x (xx.xx)
Median	xx.x
Min, Max	xx,xx

9. The p-values will be printed in the tables rounded appropriately to 4 decimal places and formatted as '0.xxxx'. P-values less than 0.0001 will be formatted in the tables as '<0.0001'.
10. All fractional numeric values should be printed with a zero to the left of the decimal point (e.g., 0.12, 0.3).
11. Unless otherwise specified, percentage values should be printed with one digit to the right of the decimal point (e.g., 12.8%, 5.4%).
12. Missing data should be represented on subject listings as either a hyphen ("--").
13. Dates printed as a result in the table, listing, or graph should be printed in SAS DATE9. format ("DDMONYYYY": 01 JUL 2002). Missing portions of dates should be represented on subject listings as dashes (-- JUL 99). Dates that are missing because they are not applicable for the subject should be listed as "N/A", unless otherwise specified.

6 List of Tables

Table 14.1.1	Subject Disposition, All Subjects
Table 14.1.2.1	Demographics and Baseline Characteristics, Safety Set
Table 14.1.2.2	Demographics and Baseline Characteristics, Full Analysis Set
Table 14.1.2.3	Demographics and Baseline Characteristics, Per Protocol Set
Table 14.1.3.1	Medical and Surgical History, Safety Set
Table 14.1.3.2	Medical and Surgical History, Full Analysis Set
Table 14.1.3.3	Medical and Surgical History, Per Protocol Set
Table 14.1.4	Prior Medications, Safety Set
Table 14.1.5	Concomitant Medications, Safety Set
Table 14.1.6.1	Study Drug Exposure, Safety Set
Table 14.1.6.2	Study Drug Exposure, Full Analysis Set
Table 14.1.7.1	Study Drug Compliance, Safety Set
Table 14.1.7.2	Study Drug Compliance, Full Analysis Set
Table 14.2.1.1.1	Response Based on Clinical Global Impressions – Improvement (CGI-I) as Assessed by Clinician at Week 12 Comparing OV101 and Placebo, Full Analysis Set
Table 14.2.1.1.2	Response Based on Clinical Global Impressions – Improvement (CGI-I) as Assessed by Clinician at Week 12 Comparing OV101 and Placebo, Per Protocol Set

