10.1.3.4 Early Termination

The study may be terminated at an individual study center if it becomes apparent that subject enrollment is unsatisfactory with respect to quality and/or quantity. Study centers may also be closed if they prove to be unable to comply with the requirements of the protocol or GCP, or data recording is inaccurate and/or incomplete. If the study is terminated in an individual study center for any reason, the investigator must make every effort to follow-up all subjects as planned according to the protocol. Replacement of study centers is allowed and new study centers may be initiated. An initiative for study center closure or study termination can be taken at any time either by Ovid Therapeutics

Inc. or by the investigator, provided there is reasonable cause and sufficient notice is given in advance of the intended termination.

See Section 13 for early withdrawal from study. For early withdrawal, subject should follow Week 12 study visit schedule of assessment for safety measure which include medical history, clinical assessment, ABC-C irritability subscale, physical examination, clinical lab test, serum pregnancy test, concomitant medications. Efficacy assessments do not need to be completed.

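### Carrying Week 6 forward for missing Week 12 binary outcomes can favour the arm that loses more Week 6 responders, relative to counting leavers as non-responders

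*SAP*

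**What the plan says.** SAP 3.1.2 states that selected Week 12 efficacy analyses adjust for missing values, where possible, "by using the corresponding Week 6 observations either implicitly (in MMRM analyses) or by simple imputation (for binary endpoints". It then limits the rule: "For all other analyses, observed case data will be used and no imputations for missing data will be performed". The selected analyses are said to be set out later, but SAP 3.8 is redacted. The reader cannot see which binary endpoints are covered or whether sensitivity analyses accompany them.

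The visible analysis that the rule would most naturally cover is Table 14.2.1.1.1 in SAP section 6 (List of Tables), which carries this title: "Response Based on Clinical Global Impressions – Improvement (CGI-I) as Assessed by Clinician at Week 12 Comparing OV101 and Placebo, Full Analysis Set". The same analysis is repeated on the Per Protocol Set in Table 14.2.1.1.2, and Table 14.2.1.1.4 is an MMRM of CGI-I. SAP 3.11 makes combined OV101 against placebo the main comparison. SAP 3.1 sets the testing convention: "all tests will be 2-tailed using a 0.05 level of significance".

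The protocol gives different instructions on efficacy data after early exit:

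- Section 10.1.3.4, on early withdrawal: "Efficacy assessments do not need to be completed".
- Section 11.4 asks for all end-of-study assessments where possible.
- Section 13.1.1 asks those who withdraw before End of Treatment to have that visit's procedures.
- Section 13.1.2 asks that subjects who stop study drug still be followed for efficacy if feasible.

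**The concern.** Wherever the rule applies, a subject rated a responder at Week 6 who then leaves, for intolerance or any other reason, enters the Week 12 analysis as a responder. Protocol 8.1 and 10.3 report dizziness, nausea, vomiting and somnolence more often on OV101 than on placebo in earlier studies, so unequal dropout is plausible. Protocol 10.3 gives an elimination half-life of about 1.5 hours, so a Week 6 rating made on drug is weak evidence about Week 12 status once drug has stopped.

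Two things are at stake. The responder difference may credit an arm with subjects who did not stay on treatment. Also, a single imputed value is analysed as though it had been measured, so the uncertainty in it is ignored. SAP 2.1 says the efficacy results are meant to identify parameters for later efficacy studies, and a distorted responder rate could mislead that choice.

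**Working it through.** **The plan's own figure.** The only visible design calculation is in protocol 17.1: the 95% CI half-width for an adverse event incidence of 25%. The Wald form 1.96 × √(0.25 × 0.75 / n) gives 16.97% for n = 25 and 18.98% for n = 20. The stated 17% and 19% reproduce. No visible figure concerns responder rates, dropout or efficacy power, so everything below rests on assumed rates.

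**Inputs from the documents.** SAP 2.2.1: "Approximately 75 subjects will be enrolled and randomized into one of 3 treatment groups", "with a 1:1:1 treatment allocation" (SAP 2.2.2). That is about 25 per arm, or 50 against 25 when the OV101 arms are combined. Tests are two-sided at 0.05.

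**Assumed inputs.** d is the share lost after Week 6: 10%, 16% or 20% on OV101 and 4% on placebo. r6 is the Week 6 response among those lost, 10% to 50%, taken as the same in both arms. r12 is the Week 12 response in completers, 30% in both arms.

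**Expected response rate in an arm.**

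- Carry-forward: (1 − d) × r12 + d × r6
- Missing scored as non-response: (1 − d) × r12
- Observed cases: r12

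**Shift in the OV101-minus-placebo difference.** Carry-forward minus non-response is (d_OV − d_PBO) × r6. Carry-forward minus observed cases, when r12 is equal in both arms, is (d_OV − d_PBO) × (r6 − r12).

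| Lost, OV101 vs placebo | Against non-response, r6 = 10% to 50% | Against observed cases, r6 = 10% / 30% / 50% |
|---|---|---|
| 10% vs 4% | +0.6 to +3.0 points | −1.2 / 0 / +1.2 |
| 16% vs 4% | +1.2 to +6.0 points | −2.4 / 0 / +2.4 |
| 20% vs 4% | +1.6 to +8.0 points | −3.2 / 0 / +3.2 |
| 10% vs 10% | 0 | 0 |

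**Chance of a significant result favouring OV101.** Suppose the rates with leavers scored as non-responders are truly 25% in each group. Enumerating all outcomes for 50 against 25 gives the figures below. The planned test is not visible, so two are shown.

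| Lost, r6 | Carry-forward rates | Chi-square | Fisher |
|---|---|---|---|
| none | 25.0% vs 25.0% | 2.3% | 1.7% |
| 10% vs 4%, 30% | 28.0% vs 26.2% | 3.3% | 2.6% |
| 20% vs 4%, 30% | 31.0% vs 26.2% | 5.6% | 4.7% |
| 20% vs 4%, 50% | 35.0% vs 27.0% | 9.5% | 8.5% |

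The excess is an error only if leaving is meant to count as non-response.

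**In whole subjects.** With non-response scoring, take 15/50 against 5/25: a difference of 10 points, chi-square p = 0.36. If four OV101 leavers are carried as responders and none on placebo, this becomes 19/50 against 5/25: 18 points, p = 0.12.

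**Why the comparator matters.** Assume 16% against 4% lost, r6 = 45%, and completer response of 30% against 20%.

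- Carry-forward: (0.84 × 0.30 + 0.16 × 0.45) − (0.96 × 0.20 + 0.04 × 0.45) = 32.4% − 21.0% = 11.4 points
- Non-response: 25.2% − 19.2% = 6.0 points
- Observed cases: 30% − 20% = 10.0 points

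Of the 5.4-point gap between the first two, 1.4 is carry-forward rising above observed cases and 4.0 is non-response scoring falling below them.

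**The case against.** A reader might infer that the rule favours OV101, or whichever arm has more tolerability dropouts. The documents do not support that without conditions. They give no dropout or response rates. Against observed cases the sign depends on whether leavers responded at Week 6 more or less often than completers did at Week 12, so the rule can penalise the arm with more dropout.

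A reader might also infer that every missing binary outcome is filled this way. The SAP covers selected analyses only, and the text that would show the CGI-I method and any sensitivity analysis is redacted.

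The number of subjects affected may be small. Protocol 10.1.3.2 expects slowed titration to finish by Day 21, well before the Day 43 visit, so early intolerance may leave no Week 6 value to carry. Subjects who stop drug but stay in follow-up under protocol 13.1.2 have an observed Week 12 value. This stands in part. However, the Full Analysis Set requires a post-dose efficacy evaluation, and the first scheduled post-dose clinic visit is Day 43. Most subjects who leave before that visit would therefore fall outside the set, unless diary data count. Among those who remain with Week 12 CGI-I missing, most would have a Week 6 value to carry. Protocol 12.1.3.6 also foresees intolerance throughout the 12 weeks.

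Non-response scoring is itself a single imputation. It does not cure the understated uncertainty, and it counts logistical losses as failures. That objection stands: it is a reason to show several analyses, not to make non-response scoring the only main one.

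The Per Protocol table and the MMRM add information, but neither is a check on this point. The Per Protocol Set contains only Week 12 completers, and the MMRM is not a responder analysis.

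**Conclusion.** The point holds in conditional form. Where the rule applies, Week 6 responders who leave later are scored as Week 12 responders whatever their reason for leaving. Relative to counting leavers as non-responders, this moves the treatment difference towards an arm that loses more Week 6 responders after Week 6. The movement is about 0.6 to 8 points for assumed dropout of 10% to 20% against 4% and assumed Week 6 response of 10% to 50%, and nil with equal dropout and equal leavers' response. Relative to observed cases, with r12 at 30% in both arms, it runs from −3.2 to +3.2 points over the same range. Carried values are treated as observed in either case.

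The documents do not show that the trial's responder result is biased towards OV101. They show that a conclusion resting on carry-forward alone would depend on an untested assumption that Week 6 status persists. Efficacy is not the primary objective, and the primary safety analysis is unaffected.

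**What to change.** In SAP 3.1.2, state that the conclusion on Week 12 binary response, for example CGI-I, will not rest on Week 6 carry-forward alone. On the Full Analysis Set, report beside it:

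- the response analysis with missing Week 12 scored as non-response; and
- the analysis with multiple imputation using Week 6 response as a predictor, which also carries the imputation uncertainty into the standard errors.

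If the redacted text already does this, nothing more is needed on the analysis. The cost is a short SAP edit and one or two extra tables. Response rates will be slightly lower under non-response scoring.

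Separately, protocol 10.1.3.4 must be reconciled with 11.4, 13.1.1 and 13.1.2 on efficacy assessments after early withdrawal or drug discontinuation, because these sections determine how often the rule is used.
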